The chosen study design is a propensity score-matched retrospective cohort study. This is one of the best pharmaco-epidemiological designs available for the assessment of intended (benefits) and unintended (risks) effects of drugs in observational data. Propensity score-matching will therefore be used to match each eligible bisphosphonate user to 5 non-users, producing matched comparable (in terms of observed baseline characteristics) cohorts.

TARGET POPULATION

The target population of this study will be patients with an eGFR<45 (based on serum creatinine) aged 40 years or older at the age of biochemistry testing.

EXCLUSION CRITERIA

From the population described above, we will exclude those with any of the following exclusion criteria:

- Less than 1 year of follow-up data available within the data source/s.
- CPRD participants with no possible linkage to HES.
- Use of anti-osteoporosis medication/s in the previous year (except calcium and/or vitamin D supplements).
- Use of any (except calcium and/or vitamin D supplements) other anti-osteoporosis medication/s (other than bisphosphonates).

SETTING/CONTEXT

Setting: The proposed study will obtain data from both primary (CPRD) and secondary (HES) care.

Study period: Currently used oral bisphosphonates (alendronate, risedronate and ibandronate) were approved and launched to the market in 1996 onwards. Our study period will therefore cover from 1996 to the latest data extraction for the identified data sources, likely 31/12/2014.

Follow-up: Data from randomized placebo-controlled trials have shown that bisphosphonates are effective to reduce fracture risk only after at least 6 months of continuous use (27). That is not the case though for adverse events, which can be observed immediately after bisphosphonate therapy initiation (14, 17, 28). Therefore, different follow-up windows will be established, as follows:

- Safety outcomes (WP1 and WP3): Patients will be followed from the latest of the following dates
- a) Start of study period
- b) One year of valid data in database
- c) Date of incident prescription of bisphosphonate (after one year of non-use)

until the earliest date of:

- a) The end of enrolment in the database (due to moving out or death)
- b) Date of last data update in the database
- c) Stopping of treatment +30 days (no repeat prescription within 1 month)
- d) Switch of treatment to other (non-bisphosphonate) osteoporosis medication

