- e) Outcome of interest (different date for each study outcome)
- Effectiveness outcomes (WP2 and WP4): Patients will be followed from the latest of the following dates
- a) Start of study period
- b) One year of valid data in database
- c) Date of continued prescriptions of an oral bisphosphonate for 6 months after the date of therapy initiation

until the earliest date of:

- a) The end of enrolment in the database (due to moving out or death)
- b) Date of last data update in the database
- c) Stopping of treatment +180 days (no repeat prescription within 6 months)
- d) Switch of treatment to other osteoporosis medication, with no repeat prescription of oral bisphosphonates within the next 6 months
- e) Incident recorded fracture (WP2) or last BMD measurement available (WP4)

SAMPLING

One of the advantages of routinely collected datasets is that the contained information is readily available, not needing active recruitment. Therefore, all patients eligible (see target population and exclusion criteria above) registered in the chosen data sources will be included.

Sample size/power: According to feasibility counts provided by CPRD, the number of eligible patients (with an eGFR<45 and possible to link to HES) would be of 204,528 subjects, and 34,127 (16.7%) of these received oral bisphosphonate prescriptions. These numbers would provide statistical power to reliably answer each of the study aims, as it can be seen below:

Work-package 1: In a survival analysis (log-rank 2-sided test), accepting 5% type I error and 20% attrition from propensity score matching and loss to follow-up in 2 years, and assuming CKD stage progression rates of 12/100 person-years (29), the available number of participants would provide 90% power to detect an excess risk of CKD progression of 10% or more (HR \geq 1.10) associated with oral bisphosphonate use.

Work-package 2: In a log-rank (2-sided) test, and accepting 5% type I error and 20% drop-out, with 2 years of follow-up and an expected fracture rate of 103/10,000 person-years in CPRD data (30), the available sample size would provide 90% power to detect a fracture reduction of at least 15% (HR≤0.85) amongst oral bisphosphonate users (compared to non-users).

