Propensity Score matching: Propensity scores represent the probability that a patient will receive the drug of interest (i.e. oral bisphosphonates) according to their baseline sociodemographics and clinical characteristics. Multivariable logistic regression equations will be used to calculate one propensity score for each of the study outcomes of interest (36). Prespecified predictors of each of these outcomes will be included in each of these equations (37). Finally, the created propensity scores will be used to match bisphosphonate users to comparable non-users with a caliper matching technique with a maximum caliper width of 0.02 standard deviations (SDs). In short, this means that bisphosphonate non-users will only eligible to be matched if their propensity score falls within a bandwidth of 0.02 SDs of the bisphosphonate user subject's propensity score. This method has been shown to be the most efficient to minimize confounding by indication in pharmacoepidemiological studies (6) and typically excludes the small proportion of patients with extremely high or extremely low risk

for the outcome that are not present in both intervention and comparator patient samples. Covariate balance achieved through PS matching will be assessed using absolute standardized difference in means or proportions.

Some confounders, such as smoking, alcohol drinking, body mass index might not be completed. We will impute them for the propensity score (logistic) models using multiple imputation by chained equations (MICE) methods. 10 imputed datasets will be used. For each imputed dataset, a ps matched dataset will be identified and analysed as per study outcome separately. Outcome estimates of 10 ps imputed datasets will be then combined using Rubin's rules to obtain an overall outcome estimate (46).

Absolute rates of study outcomes: The crude and age and sex specific incidence rates (and 95% confidence intervals) of each of the events will be estimated separately in the cohort of oral bisphosphonate users and amongst propensity score-matched non-users assuming a Poisson distribution. Kaplan-Meier plots will be created to show the predicted cumulative probability of each of the study endpoints according to bisphosphonate use.

In addition, annualized eGFR (secondary outcome in WP1) and BMD (WP4) changes and 95% confidence intervals will be reported.

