Immortal time bias and time-varying exposure: Immortal time bias (ITB) is a common issue in pharmaco-epidemiology. In brief, ITB appears when in a study the event of interest cannot occur for a certain time span due to study design and/or data analysis methods used (26). In cohort studies, immortal time typically arises when the definition of drug use involves a delay or wait period during which follow-up time is accrued—for example, waiting for a prescription or drug dispensation after discharge from hospital when the discharge date represents the start of follow-up (38).

A number of methods are available to avoid ITB. We will, in our study, use time-varying exposures, where in a survival analysis the time previous to index date for drug users (i.e. the time before first prescription of oral bisphosphonates) is reclassified as drug non-user personyears. We have extensive expertise using this method (39-41), which has been shown to be the most efficient to avoid ITB in pharmaco-epidemiological studies (42).

Hazard ratios: We will use proportional hazards Cox regression modelling to estimate the Hazard Ratio (HR) and 95% Confidence Intervals for each of the outcomes of interest according to bisphosphonate use. To account for the matched cohort approach proposed, we will use Cox regression stratified by matched sets.

The proportional hazards assumption will be checked using clog log plots. Alternative models, e.g. parametric survival models and weighted Cox regression(43) will be considered. The final decision of the alternative modelling techniques will depend on the availability of a suitable function to describe the hazards distribution.

If mortality rates are different amongst bisphosphonate users and matched non-users, Fine and Gray survival analyses (44) will be used instead, to account for a competing risk with death.

Failing to do so would results in a biased estimation of the excess/reduced risk of the events of interest amongst bisphosphonate users (45).

Beta coefficients: Longitudinal analysis will be used to study the association between bisphosphonate use and annualized changes of both eGFR (secondary outcome in WP1) while linear regression modelling will be used to study the association between bisphosphonate use and changes of BMD between two observed time points (WP4). Beta coefficient and 95% confidence intervals will be reported for the effect of bisphosphonate use on both outcomes.

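### Replacing the Cox hazard ratio with Fine-Gray when mortality differs lets a mortality gap pass for a drug association, and the Kaplan-Meier plots overstate cumulative risk

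*Protocol*

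**What the plan says.** All places are in the protocol.

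- **Data analysis, Hazard ratios.** The default is clear: "we will use Cox regression stratified by matched sets". The conditional rule follows: "If mortality rates are different amongst bisphosphonate users and matched non-users, Fine and Gray survival analyses (44) will be used instead". The reason given is: "Failing to do so would results in a biased estimation of the excess/reduced risk of the events of interest amongst bisphosphonate users (45"). Nothing says that the Cox ratio is kept alongside.
- **Data analysis, Absolute rates of study outcomes.** Poisson incidence rates with confidence intervals are planned, and also: "Kaplan-Meier plots will be created to show the predicted cumulative probability of each of the study endpoints according to bisphosphonate use". No competing-risk version of the curves is mentioned.
- **Setting/context, Follow-up.** For both safety and effectiveness outcomes, one of the events that end follow-up is: "The end of enrolment in the database (due to moving out or death"). Death and moving away are treated as the same kind of exit.
- **Data analysis, Propensity score matching.** On what enters the scores: "Prespecified predictors of each of these outcomes will be included in each of these equations (37"). Death is not one of the study outcomes.
- **Aims and objectives.** Work-packages 1 to 3 ask whether oral bisphosphonate use is associated with CKD progression, fracture and adverse events.

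**The concern.** Two quantities are being treated as substitutes. The cause-specific hazard ratio, which Cox regression estimates when death is censored, compares event rates among patients still alive and at risk. The sHR keeps patients who have died in the risk set, so it describes how the cumulative proportion with the event differs. If fewer users die, more of them live long enough to progress or fracture, and the sHR rises above 1 with no effect of the drug on bone or kidney. If more users die, it falls below 1.

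The protocol swaps one for the other when mortality differs, which is the only condition under which they diverge for this reason. A reader would then see a single ratio and could not tell how much of it is death. The mortality gap may itself be confounded, because the propensity scores are built from predictors of the study outcomes. The results are intended for regulators and guideline bodies, who would read the ratio as harm or benefit of the drug.

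Competing death does distort the cumulative probability curves, and there the protocol leaves it unaddressed.

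**Working it through.** **Inputs from the protocol (Sampling).** The eligible population "would be of 204,528 subjects", of whom 34,127 are users; 1:5 matching; 20% loss; 2 years; two-sided 5%; CKD progression 12 per 100 person-years; fracture 103 per 10,000 person-years.

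**Assumed, because the protocol gives no mortality rate.** Non-user mortality of 5 to 20 per 100 person-years; user/non-user mortality ratio of 0.7 to 1.2; constant hazards; full 1:5 matching.

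**1. The plan's own figure.** For fracture (work-package 2), after 20% loss there are 27,302 users and 136,508 non-users.

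- Events at HR 0.85: 27,302 × (1 − exp(−2 × 0.0103 × 0.85)) + 136,508 × (1 − exp(−2 × 0.0103)) = about 3,257.
- Freedman's formula with allocation 0.2: √(3,257 × 0.2) × 0.15 / (1 + 0.2 × 0.85) − 1.96 = 1.31, so power is 90.5%.

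The stated 90% reproduces, so the survival inputs are used as they stand.

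**2. The sHR when the drug does nothing to the event.** With event hazard λ and death hazard μ:

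- F(t) = λ/(λ+μ) × (1 − exp(−(λ+μ)t))
- subdistribution hazard = λ exp(−(λ+μ)t) / (1 − F(t))

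Take CKD progression with λ = 0.12 in both groups and deaths of 10 (non-users) against 7 (users) per 100 person-years. At time 0 the ratio is 1. At 2 years it is (0.0821/0.8003) / (0.0773/0.8058) = 0.1025/0.0959 = 1.07. Averaged over 2 years by solving the Fine-Gray score equation at 1:5 allocation, the sHR is 1.03; over 5 years it is 1.07 to 1.08. The cause-specific ratio is exactly 1 throughout.

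Over the assumed range (each cell runs from non-user mortality 5 to 20 per 100 person-years):

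| Outcome, horizon | Mortality ratio 0.7 | 1.0 | 1.2 |
|---|---|---|---|
| Fracture, 2 years | 1.015 to 1.058 | 1.000 | 0.990 to 0.964 |
| CKD progression, 2 years | 1.015 to 1.060 | 1.000 | 0.990 to 0.963 |
| Fracture, 5 years | 1.037 to 1.138 | 1.000 | 0.976 to 0.921 |
| CKD progression, 5 years | 1.039 to 1.138 | 1.000 | 0.975 to 0.922 |

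A simulated check (fracture, 5 years, 10 against 7 deaths, 300,000 patients) gave Cox 1.039 and Fine-Gray 1.113, each with a standard error of 0.024 on the log scale. Their ratio of 1.072 matches the analytic sHR of 1.072.

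A true fracture ratio of 0.85, with non-user mortality of 10 per 100 person-years, becomes 0.875 at 2 years if the mortality ratio is 0.7, and 0.834 if it is 1.2.

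**3. How often the shift would be nominally significant** (2 years, 10 against 7 deaths, no drug effect on the event). The expected test statistic is √(D × 1/6 × 5/6) × ln(sHR), where D is the number of events.

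- CKD progression: D = 27,302 × 0.1997 + 136,508 × 0.1942 = about 31,960. Then √(31,960 × 0.1389) × 0.0296 = 1.97, so about half the time.
- Fracture: D = about 3,043. Then √(3,043 × 0.1389) × 0.0296 = 0.61, so about 9% rather than 5%.

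For non-user mortality of 5 to 15 per 100 person-years and ratios of 0.7 to 0.8, the range is 11% to 82% for CKD progression and 5.5% to 14% for fracture.

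**4. Kaplan-Meier against cumulative incidence** (CKD progression, deaths at 10 per 100 person-years).

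- 2 years: 1 − exp(−0.24) = 21.3%, against 0.12/0.22 × (1 − exp(−0.44)) = 19.4%.
- 5 years: 45.1% against 36.4%.

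For fracture at 2 years, Kaplan-Meier overstates cumulative incidence by a relative 5% to 21% for mortality of 5 to 20 per 100 person-years.

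**The case against.** The best defence is that risk in the presence of death is a legitimate target. The protocol speaks of risks and benefits, and prescribers and regulators may want exactly that quantity. Fine-Gray addresses it, and the sentence about bias is defensible for cumulative risk. This stands, and it is why Fine-Gray should be kept as a companion measure. It does not justify removing the cause-specific ratio, nor calling that ratio biased for the association it estimates.

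Several stronger readings are tempting but not supported:

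- *That a false signal is nearly certain.* A reader might set a 5-year sHR of 1.07 against the roughly 35,400 CKD events expected in 2 years and get a rejection rate of about 99%. Those figures belong to different horizons; at 2 years the rate is about half. With full 5-year follow-up it would approach certainty for CKD progression, but safety follow-up ends 30 days after treatment stops and no persistence figure supports 5 years.
- *That any small mortality gap triggers the switch.* No test or threshold is stated, and that detail may be in the analysis plan. Small gaps also give small shifts: 10 against 9 deaths per 100 person-years gives 1.01 at 2 years.
- *That the drug would always look worse.* This holds only if users die less; the reverse gap flatters it.
- *That all reported absolute risks are too high.* The Poisson rates per person-time are not inflated in this way. Only the curves, read as cumulative probabilities, are affected.
- *That Fine-Gray cannot be combined with the planned exposure definition.* The plan is to "use time-varying exposures, where in a survival analysis the time previous to index date for drug users" count as non-use, so exposure changes once, from non-use to use. A user who dies remains a user; ambiguity is confined to non-users who die before a possible start. Nor does the protocol say that matched-set stratification is dropped under Fine-Gray.

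The event counts are also upper bounds: 5 × 34,127 = 170,635 non-users are needed, but 204,528 − 34,127 = 170,401 exist before the caliper removes any.

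**Conclusion.** The point holds as a fault in the rule as written. The protocol replaces a measure that answers its stated aims with one that mixes in mortality, does so when the two differ, and gives a reason that is wrong for those aims.

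The size is modest at the 2-year planning horizon, up to about 6% on the hazard ratio, and grows to about 14% at 5 years. It can go either way and is zero when mortality is equal. It matters most for work-package 1, which is planned around a hazard ratio of 1.10 and has enough events for a 3% shift to be nominally significant about half the time. For fracture the corresponding figure is about 9%. All of this rests on assumed mortality, constant hazards, full 1:5 matching and 20% loss.

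The Kaplan-Meier point is separate. Its direction is certain whenever any patient dies before the event; its size again depends on the assumed mortality.

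**What to change.** - Keep the matched-set cause-specific Cox hazard ratio as the main association measure for every outcome in work-packages 1 to 3, whatever the mortality.
- Report beside it the cause-specific hazard ratio for death and the Fine-Gray sHR, the latter labelled as a measure of cumulative risk.
- Replace the Kaplan-Meier plots with Aalen-Johansen cumulative incidence curves, with death as the competing event.
- In the Hazard ratios paragraph, delete the word *instead*, and restrict the sentence about bias to estimates of cumulative risk.

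The cost is a change of wording, standard software output and one extra table. No new data are needed, since death already ends follow-up in the plan.

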DISSEMINATION AND PROJECTED OUTPUTS
OUTPUTS
DISSEMINATION
MANAGEMENT PLAN
REGULAR COMMUNICATION
APPROVAL BY ETHICS COMMITTEES
PATIENT AND PUBLIC INVOLVEMENT26
REFERENCES
APPENDIX 1

SUMMARY OF RESEARCH

AIM/S

Although osteoporosis and fragility fractures are common amongst CKD patients, the effectiveness and safety of first-line anti-fracture therapies (bisphosphonates) for this population are still unclear. We therefore aim to study the association between oral bisphosphonate (OB) use in stage ≥3B CKD patients and the following outcomes: CKD progression (stage worsening or entering renal replacement therapy or transplant) (WP1), clinical fracture/s (WP2), adverse events (hypocalcaemia or hypophosphatemia, upper gastro-intestinal events, and acute kidney injury) (WP3), and axial bone mineral density (WP4).

METHODS

Data sources: the primary data source for WP1-3 of our study will be the Clinical Practice Research Datalink (CPRD), linked to the Hospital Episodes Statistics (HES). Data from the Danish Odense University Hospital Database (OUHD) will be used for WP4.

Study participants: all patients registered in CPRD or in OUHD, aged \geq 40 years, with an eGFR<45, and with \geq 1 years of follow-up data available will be included. Users of bisphosphonates in the year before eGFR testing, as well as CPRD participants with no possible linkage to HES data will be excluded.

Exposure: Users of oral bisphosphonates will be identified from primary care prescriptions (CPRD) or pharmacy dispensations (OUHD).

Outcomes: WP1: CKD progression will be defined as stage worsening (according to eGFR as recorded in CPRD) or initiation of renal replacement therapy/transplant (HES).

Study outcomes for WP2-3 will be ascertained using previously validated lists of READ/OXMIS (CPRD) (1-3) or ICD-10/OPCS (HES) (4) codes. The main study outcomes will be: all clinical fractures excluding the skull/face and digits, which are not considered to be osteoporotic (WP2), and adverse events (hypocalcaemia/hypophosphatemia requiring hospital admission, upper gastro-intestinal events, and hospitalization for acute kidney injury) for WP3. WP4: annualized hip bone mineral density percentage change, as measured using DXA scan, will be measured.

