In summary, the proposed study would have \geq 90% power to detect as significant an excess risk of \geq 10% between bisphosphonate use and both upper GI and hypocalcaemia/hypophosphatemia events, and of (in the most conservative scenario) \geq 40% between use of bisphosphonates and risk of AKI.

Work-package 4: The Danish OUHD included 35,025 patients in the year 2012. We expect to identify at least 500 CKD patients defined as oral bisphosphonate users, matched 1:5 to 2,500 non-users. Accepting type I error of 5% in a two-sided test, and a common mean (standard deviation) hip BMD loss of 0.61% (1.23%) per year (34), this sample size would provide >80% power to detect as significant a >25% difference in bone loss change between bisphosphonate users and non-users.

DATA COLLECTION

Data linkage and management: As stated above, one key advantage of routinely collected data is the immediate access to large and representative samples of patients with no need for prospective data collection. In our proposal, over 200,000 eligible patients (with an eGFR<45) have been identified in CPRD, with >34,000 of them starting bisphosphonate use in the study period.

More challenging is however the workload involved in the linkage and data management required for the current study, where 2 different data sources (CPRD and HES) will be linked to answer the aims of WP1-3. For this reason we have included co-applicants with extensive experience in linkage between these data sources as described above (see "Response to feedback points"). The data management needed to produce a final working dataset will be carried out by a senior data manager at Oxford with expertise in such procedures. With supervision from the PI and the appointed statistician, she will develop ad-hoc code in Python and SQL to produce a dataset that can be analyzed using standard statistical packages such as Stata.

For WP4, investigators at the Odense Patient Data Exploratory Network (OPEN) initiative will carry out the linkage of clinical (including bone mineral density), biochemistry (i.e. serum

creatinine), and pharmacy dispensations data, as well the needed data management. The funding for these are either included in the requested data license fee (linkage and data management) or provided at no cost by external collaborators (supervision by [name] and [name]).

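### WP4 (BMD change) inherits a six-month delayed start justified only by fracture effect, and neither scan rule ties the first BMD measurement to treatment start

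*Protocol*

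**What the plan says.** The WP4 outcome (Protocol, Summary of Research, Outcomes) is "annualized hip bone mineral density percentage change, as measured using DXA scan". The model is given in one sentence under Data Analysis, Beta coefficients: "linear regression modelling will be used to study the association between bisphosphonate use and changes of BMD between two observed time points (WP4". No rule there fixes either time point.

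The timing rules are under Setting/Context, Follow-up. WP4 is grouped with fractures: "Effectiveness outcomes (WP2 and WP4): Patients will be followed from the latest of the following dates". The third of those dates is "Date of continued prescriptions of an oral bisphosphonate for 6 months after the date of therapy initiation". For WP4 the outcome-related end date is "last BMD measurement available (WP4".

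The reason for the delayed start opens the same section: "bisphosphonates are effective to reduce fracture risk only after at least 6 months of continuous use (27". No separate reason is given for BMD.

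On confounding control, the Propensity Score matching paragraph provides one score per outcome: "Prespecified predictors of each of these outcomes will be included in each of these equations (37". Users are matched 1:5 and balance is checked by standardized differences. The list of predictors for WP4 is not shown.

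**The concern.** A change outcome is defined by its two measurements. If the first lies inside a window that opens six months into treatment, the comparison is between later on-treatment change in users and change over some other period in non-users. It is no longer the change that follows starting the drug. A six-month wait may suit an outcome on which the drug is thought not to act earlier, and the protocol makes that argument for fractures. It makes no such argument for BMD.

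The delayed start also has no counterpart in non-users. The first two start dates (start of study period, one year of valid data) can apply to them, but the third cannot, because it depends on prescriptions they never had. The time-varying exposure device in the immortal-time paragraph is described for survival analysis and does not supply a start date for the WP4 linear regression.

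At stake is what the WP4 coefficient measures, and whether users and matched non-users are measured over comparable periods.

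**Working it through.** **1. The rules side by side.**

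| Item | Users | Matched non-users |
|---|---|---|
| Start of WP4 follow-up | six months of continued prescriptions, if later than the other two dates | only the study-period and one-year-of-data dates can apply |
| First scan | not stated; on treatment if it must lie in the window | not stated |
| Last scan | last BMD measurement available, subject to the other end dates | last BMD measurement available |
| Reason for the lag | fracture effect only | none |

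**2. What the lag can do to the annualized difference.** Let E be the user-minus-non-user difference in percentage BMD change over the first six months, L the yearly difference afterwards, and T the years from treatment start to the last scan. Suppose both groups are scanned on the same clock and the first in-window scan falls at exactly six months.

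- From a scan at treatment start: (E + L(T − 0.5)) / T
- From the first in-window scan: L
- Difference: (E − 0.5L) / T

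If the early response runs at the later rate (E = 0.5L), the annualized figure is unchanged. If it is faster, the in-window figure understates the effect; if slower, it overstates it. The protocol gives neither E nor L, so no size can be stated. For scale, with T = 2 years (assumed), the shift equals the WP4 target when E exceeds 0.5L by 2 × 0.1525 = 0.305% of BMD.

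**3. The target.** Sampling, Work-package 4, gives a mean hip BMD loss of 0.61% per year and a 25% difference to be detected: 0.25 × 0.61 = 0.1525 %/year.

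**4. Why baseline BMD matters once a pre-treatment scan is used.** If a low reading leads to treatment, part of the low value is measurement error and reverts on re-measurement. When treatment depends on the measured value:

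spurious gain per year = (1 − reliability) × observed baseline gap in SD × SD as % of mean / years between scans

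All inputs are assumed, since the protocol gives none: SD 15% of the mean, reliability 0.97 to 0.99, users 0.25 to 1 SD lower, scans two years apart.

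| Case | Calculation | %/year | Share of 0.1525 |
|---|---|---|---|
| Low | 0.01 × 0.25 × 15 / 2 | 0.019 | 0.12 |
| Middle | 0.02 × 0.5 × 15 / 2 | 0.075 | 0.49 |
| High | 0.03 × 1 × 15 / 2 | 0.225 | 1.48 |

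Widening reliability to 0.95 to 0.99 and the interval to one to three years gives 0.01 × 0.25 × 15 / 3 = 0.013 up to 0.05 × 1 × 15 / 1 = 0.75 %/year. These figures apply only if the first scan precedes treatment and baseline BMD is neither balanced by matching nor adjusted for.

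**The case against.** The Follow-up section defines follow-up dates and the Beta coefficients paragraph says only that there are two time points. Neither states that the first scan must lie inside the window, so the analysts may intend a pre-treatment scan. That is possible, but then the delayed start does no work for WP4. The text as written leads a reader to the on-treatment scan. The ambiguity is itself what needs fixing.

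A reader might infer that the plan omits baseline BMD. The document does not support this. It provides an outcome-specific propensity score with pre-specified predictors, the list is not shown, and such lists are commonly left to the SAP. Baseline BMD may well be in the WP4 score, and matching on it would largely remove the regression-to-the-mean bias. What remains is that a score needs a pre-treatment value, and the protocol does not define one for WP4.

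It is also fair to say that adjustment is not automatically safe. If users' true BMD is lower for reasons other than the measured value, adjusting for an error-prone baseline brings in a bias of the same form, (1 − reliability) × gap, with the opposite sign. Change score against baseline adjustment is therefore a judgement. Adjustment is favoured here to the extent that a measured low value prompts treatment.

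Finally, the regression-to-the-mean range is about twelvefold and rests wholly on assumptions. That stands: it shows that the bias could matter, not that it does.

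**Conclusion.** The point holds as a timing fault. The protocol applies a fracture-based six-month delay to BMD change, does not tie the first scan to treatment start, and gives matched non-users no equivalent start date. Followed as written, the first six months of BMD change are excluded. The size and direction of the effect depend on whether early response is faster or slower than later response, which the document does not show.

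A reader might infer that lost early response and regression to the mean act together. For a given first scan they largely exclude each other: a pre-treatment scan loses no response, and a scan six months into treatment is not the reading that prompted treatment. Regression to the mean therefore supports how the corrected baseline should be handled and is not a second fault of the rule as written. On the assumptions shown it would be about 0.02 to 0.23 %/year, against the 0.15 %/year target. WP4's power statement is a separate question and is not relied on here.

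**What to change.** - Remove WP4 from the six-month window and give it its own timing rule.
- Define baseline as the last hip scan on or before the index date, the index date being the first bisphosphonate dispensing. Assign each matched non-user the index date of their user.
- Define the follow-up scan in the same way for both groups.
- Enter baseline hip BMD in the WP4 propensity score and in the linear model, and say so in the protocol.
- Keep an on-treatment first scan only as a sensitivity analysis. Because adjustment for a noisy baseline is a judgement, also report the change score with baseline BMD left out of both score and model.

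Cost: patients without a pre-index hip scan are dropped or analysed separately, and the document does not show how many that is. Entering baseline BMD needs no new data, since the scan is already part of the change outcome.
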